## 6 Treatment

### 6.1 Study treatment

#### 6.1.1 Investigational and control drugs

Investigational/control drug (name and strength)	Pharmaceutical dosage form	Route of administration	Supply type	Sponsor (global or local)
sacubitril/valsartan 50 mg	Film-coated tablets	Oral	Open label participant packs	Sponsor (local)
sacubitril/valsartan 100 mg	Film-coated tablets	Oral	Open label participant packs	Sponsor (local)
sacubitril/valsartan 200 mg	Film-coated tablets	Oral	Open label participant packs	Sponsor (local)
enalapril 5 mg	Tablets	Oral	Open label participant packs	Sponsor (local)
enalapril 10 mg	Tablets	Oral	Open label participant packs	Sponsor (local)
sacubitril/valsartan (LCZ696) in dose levels of 50 mg, 100 mg, and 200 mg are equivalent to sacubitril/valsartan 24/26 mg, 49/51 mg and 97/103 mg, respectively				

## Titration Period

After Screening and a 36-hour washout (for participants randomized to sacubitril/valsartan previously treated with ACEIs), all eligible participants will enter a Titration Period, during which they will be treated with sacubitril/valsartan (50 mg or 100 mg BID) or enalapril (2.5 mg or 5 mg BID). Participants entering the study and being treated with target dosage of ACEi/ARBs (Table 3-2) before randomization, if randomized to the enalapril arm, do not need to be down-titrated and can enter the study directly at Dose Level 3 of the titration period: enalapril 10 mg BID.

The study drugs will be provided as follows:

- enalapril 5 mg tablets to be split in half (enalapril Dose Level 1)
- enalapril 5 mg tablets (enalapril Dose Level 2)
- enalapril 10 mg tablets or 2 tablets of enalapril 5 mg (enalapril Dose Level 3)
- sacubitril/valsartan 50 mg film-coated tablets (sacubitril/valsartan Dose Level 1)
- sacubitril/valsartan 100 mg film-coated tablets (sacubitril/valsartan Dose Level 2)
- sacubitril/valsartan 200 mg film-coated tablets (sacubitril/valsartan Dose Level 3)

Participants will be required to take enalapril or sacubitril/valsartan BID at the corresponding dose level in addition to their conventional concomitant drug therapy (except for ACEIs or ARBs, which will be substituted by the study drug).

## Follow-up Period

The study drugs will be provided as follows:

- enalapril 10 mg tablets or 2 tablets of enalapril 5 mg (enalapril Dose Level 3)
- sacubitril/valsartan 200 mg film-coated tablets (sacubitril/valsartan Dose Level 3)

Based on the defined safety and tolerability criteria, participants who do not tolerate the target dosage (sacubitril/valsartan 200 mg BID or enalapril 10 mg BID) will be titrated down to the lower dose level, at the Investigator's discretion.

Sacubitril/valsartan and enalapril will be provided in blister packs or bottles.

### 6.1.2 Additional study treatments

No other treatment beyond investigational drug and control drug are included in this study.

### 6.1.3 Treatment arms

Participants eligible for Randomization at Visit 101 will be assigned to one of the following treatment arms in a 1:1 ratio:

- sacubitril/valsartan 200 mg BID
- enalapril 10 mg BID

#### **6.1.4 Treatment duration**

The study will end when at least 302 events have occurred (CV death or first hospitalization for HF) and when all participants have a minimum follow up of 3 months. Based on the planning assumptions (see [Section 12.8](#)) the overall study duration estimated to achieve the 302 events will be approximately 36 months, with a projected recruitment period of approximately 18 months and a follow-up period of 18 months after the enrollment of the last participant.

### **6.2 Other treatments**

No additional treatment is included in this study.

#### **6.2.1 Concomitant therapy**

All medications, procedures, and significant non-drug therapies (including physical therapy and blood transfusions) administered after the participant is enrolled in the study must be recorded on the appropriate eCRF.

Each concomitant drug must be individually assessed against all exclusion criteria/prohibited medication. If in doubt, the Investigator should contact the ARO medical monitor before randomizing a participant or allowing a new medication to be started. If the participant is already enrolled, contact ARO to determine if the participant should continue participation in the study.

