## Glossary of terms

Assessment	A procedure used to generate data required by the study
Biologic samples	A biological specimen including, for example, blood (plasma, serum), saliva, tissue, urine, stool, etc. taken from a study participant
Control drug	A study drug (active or placebo) used as a comparator to reduce assessment bias, preserve blinding of investigational drug, assess internal study validity, and/or evaluate comparative effects of the investigational drug
Dosage	Dose of the study treatment given to the participant in a time unit (e.g., 2.5 mg, twice a day [BID])
Electronic data capture	Electronic data capture (EDC) is the electronic acquisition of clinical study data using data collection systems, such as Web-based applications, interactive web response systems (IWRS) and clinical laboratory interfaces. EDC includes the use of electronic case report forms (eCRFs) which are used to capture data transcribed from paper source forms used at the point of care.
End of the clinical study	The end of the clinical study is defined as the last visit of the last participant or at a later point in time as defined by the protocol.
Enrollment	Point/time of participant entry into the study at which informed consent must be obtained
Investigational drug/treatment	The drug whose properties are being tested in the study
Low dosage of angiotensin-converting enzyme inhibitors (ACEIs) or angiotensin receptor blockers (ARBs)	Less than 50% of the target dosage of background ACEIs or ARBs, i.e., enalapril 2.5 mg BID as opposed to 5 mg BID. These participants should start the study at the minimum dosages of study drugs (enalapril 2.5 mg BID or sacubitril/valsartan 50 mg BID)
Medication number	A unique identifier on the label of medication kits
Mis-randomized participants	Mis-randomized participants are those who were not qualified for randomization and who did not take study treatment, but have been inadvertently randomized into the study
Naïve patients	Patients who are not receiving lifesaving drugs (e.g., newly diagnosis)
Other treatment	Treatment that may be needed/allowed during the conduct of the study (concomitant or rescue therapy)
Patient	An individual with the condition of interest for the study
Period	The subdivisions of the study design (e.g., Follow up) which are described in the protocol. Periods define the study phases and will be used in clinical study database setup and eventually in analysis

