### 3.2.2 Follow-up Period

After titration, all participants will receive Dose Level 3 of study drugs at the target dosages (sacubitril/valsartan 200 mg BID or enalapril 10 mg BID) if they tolerate them. Dose Level 3 should be maintained until the end of the study.

Participants who no longer tolerate the target dosages at any time during the course of the Follow-up Period may be down-titrated to the nearest lower dosage at the Investigator's discretion.

Before considering down-titrating the dosage of study drug to the nearest lower dose level, the Investigator should consider reducing non-disease-modifying medications (e.g., calcium channel blockers, diuretics, nitrates, and  $\alpha$ -blockers) to rectify the situation. Every attempt should be made to re-challenge the participants so that they are kept on the maximal tolerated dose of study drug for as long as possible throughout the Follow-up Period.

If study drug is temporarily discontinued, it should be reintroduced as soon as it is medically justified. Study drug discontinuation for any reason after Randomization, will not constitute withdrawal from the study. Participants are expected to attend all the protocol-specified study visits to perform all assessments as stipulated in the visit schedule, unless they do not want to continue in the study or withdraw consent. For participants who do not wish to continue with the protocol specified assessments, before withdrawn completely from the study, should be offered some modified follow-up, e.g., by less frequent visits, a final in-person visit with telephone follow-up for other planned visits, telephone follow-up alone, follow-up through contact with the primary care physician or through medical records etc.

The study will end when at least 302 events have occurred (CV death or first HF hospitalization) and when all participants have a minimum follow up of 3 months. However, based on the planning assumptions (see [Section 12.8](#)) the overall study duration estimated to achieve the 302 events will be approximately 36 months, with a projected recruitment period of approximately 18 months and a follow-up period of 18 months after the enrollment of the last participant.

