### **6.2.2 Prohibited medication**

Concomitant use of open-label ACEIs, ARBs, commercially available sacubitril/valsartan, or renin inhibitors is strictly prohibited while the participant is receiving study drug in any study epoch.

If the Investigator believes that use of one of these drugs is necessary, then study drug must be discontinued. Attention should be given to guarantee at least 36-hour washout when switching from ACEI to sacubitril/valsartan or vice-versa. If the participant is receiving enalapril and will switch to sacubitril/valsartan the enalapril must be stopped  $\geq 36$  hours prior to initiating sacubitril/valsartan. If the participant is receiving sacubitril/valsartan and will switch to any ACEI, the sacubitril/valsartan must be stopped  $\geq 36$  hours prior to initiating the ACEI. If study drug is to be re-started, the open-label ACE inhibitor or sacubitril/valsartan must also be stopped  $\geq 36$  hours prior to re-initiating study drug. ARBs or a direct renin inhibitor should be stopped prior to resuming study drug.

Concomitant administration of renin inhibitors, such as aliskiren, is prohibited.

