## **8 Visit schedule and assessments**

Assessment schedule lists all of the assessments when they are performed. All data obtained from these assessments must be supported in the participant's source documentation.

Participants should be seen for all visits/assessments as outlined in the assessment schedule or as close to the designated day/time as possible. Missed or rescheduled visits should not lead to automatic discontinuation. Participants who prematurely discontinue the study for any reason should be scheduled for a visit as soon as possible, at which time all of the assessments listed for the final visit will be performed. At this final visit, all dispensed investigational product should be reconciled, and the AEs and concomitant medications recorded on the eCRF.

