## 9 Study discontinuation and completion

### 9.1 Discontinuation

#### 9.1.1 Discontinuation of study treatment

Discontinuation of study treatment for a participant occurs when study treatment is permanently stopped for any reason (prior to planned duration), and can be initiated by either the participant or the Investigator.

The Investigator must discontinue study treatment for a given participant if, he/she believes that continuation would negatively impact the participant's well-being.

Study treatment must be discontinued under the following circumstances:

- participant decision
- pregnancy
- use of prohibited treatment as per recommendations in the prohibited treatment section
- any situation in which study participation might result in a safety risk to the participant
- any laboratory abnormalities that in the judgment of the Investigator, taking into consideration the participant's overall status, prevents the participant from continuing participation in the study

If discontinuation of study treatment occurs, the Investigator should make a reasonable effort to understand the primary reason for the participant's premature discontinuation of study treatment and record this information.

Participants who discontinue study treatment or who decide they do not wish to participate in the study further should NOT be considered withdrawn from the study UNLESS they withdraw their consent (see withdraw of informed consent section.). **Where possible, they should return for the assessments indicated** in the assessment schedule. If they fail to return for these assessments for unknown reasons, every effort (e.g., telephone, e-mail, or letter) should be made to contact the participant/pre-designated contact as specified in the lost to follow-up section. This contact should preferably be done according to the study visit schedule.

If the participant cannot or is unwilling to attend any visit(s), the study site staff should maintain regular telephone contact with the participant, or with a person pre-designated by the participant. This telephone contact should preferably be done according to the study visit schedule.

After study treatment discontinuation, at a minimum, in abbreviated visits, the following data should be collected at clinic visits or via telephone/email contact:

- new/concomitant treatments
- adverse events/SAEs

The Investigator must also contact the IWRS to register the participant's discontinuation from **study treatment**.

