2.5.1.1 Primary Estimand

An estimand is a precise description of the treatment effect reflecting the clinical question posed by the trial objective. It summarizes at a population-level, what the outcomes would be in the same patients under each of the treatment conditions being compared. Attributes of an estimand include the population, variable (or endpoint) and treatment of interest. It also specifies how intercurrent events are addressed and provides a population-level summary for the variable.

Clinical question of Interest: To assess whether sacubitril/valsartan is superior to enalapril in participants with HFrEF caused by chronic Chagas' cardiomyopathy in improving a composite hierarchical outcome.

The primary estimand is described by the following attributes:

1. **Target Population:** Adult chronic Chagas' cardiomyopathy patients with NYHA Class II-IV HFrEF (LVEF $\leq 40\%$) with or without covid-19 events.
2. **Variable:** Composite endpoint in hierarchically order
 1. Time to CV death,
 2. Time to first Heart Failure Hospitalization, and
 3. Relative change from baseline to Week 12 in NT-ProBNP.
3. **Treatment condition:** Sacubitril/Valsartan or Enalapril, regardless of the treatment switching or discontinuation and concomitant use of SGLT2 inhibitors
4. **Intercurrent event (handling strategy):**
 - Non-CV death (while alive)
5. **Summary measure:** Win ratio. Win ratio is the probability that a subject on Sacubitril/Valsartan has a better outcome than a subject on Enalapril divided by the probability that a subject on Enalapril has a better outcome than a subject on Sacubitril/Valsartan.

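### Protocol 6.2.1 lets the ARO decide whether an enrolled participant stays in the study, against the consent-only withdrawal rule; read literally, it ends follow-up early

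*Protocol*

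**What the plan says.** Protocol 6.2.1 has every concomitant drug checked against the exclusion criteria and the prohibited list. In case of doubt the investigator contacts the ARO medical monitor before randomising or before allowing a new drug. The next sentence reads: "If the participant is already enrolled, contact ARO to determine if the participant should continue participation in the study". The object of the decision is the study, not study drug. The Protocol Glossary defines enrollment as "Point/time of participant entry into the study at which informed consent must be obtained", so the sentence covers people in screening and people already randomised.

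Elsewhere the protocol handles the same situation differently:

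- Protocol 6.2.2, on the prohibited drugs: "If the Investigator believes that use of one of these drugs is necessary, then study drug must be discontinued". Washout and restart rules follow; leaving the study is not mentioned.
- Protocol 3.2.2: "Study drug discontinuation for any reason after Randomization, will not constitute withdrawal from the study".
- Protocol 6.5: if study drug is stopped completely, the participant still attends visits and is followed to study end.
- Protocol 9.1.1 lists prohibited treatment among the reasons to stop study treatment, and says that participants who stop treatment "should NOT be considered withdrawn from the study UNLESS they withdraw their consent".

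SAP 2.5.1.1 sets the treatment condition of the primary estimand as "Sacubitril/Valsartan or Enalapril, regardless of the treatment switching or discontinuation and concomitant use of SGLT2 inhibitors". SAP 2.12.1 assigns treatment policy to discontinuation and to crossover, including crossover before the endpoint.

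**The concern.** A treatment-policy estimand needs outcomes after a participant changes or stops therapy. A sentence that lets a third party end study participation because of a drug taken after randomisation works against that, and it contradicts the rule that only withdrawal of consent ends participation.

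The rest of the protocol would carry such an exit through. Protocol 8 provides that "Participants who prematurely discontinue the study for any reason should be scheduled for a visit as soon as possible", with the final-visit assessments. The Glossary entry for premature withdrawal foresees no further assessments and does not mention consent. The disposition summary in SAP 2.3.1 covers treatment discontinuation, consent withdrawal and loss to follow-up. It has no row for an exit decided by the investigator or the ARO, so such cases would be uncounted or filed under another reason. At stake are complete follow-up for CV death and HF hospitalisation, and the Week 12 NT-proBNP value. The sample size in Protocol 12.8.1 assumes no loss to follow-up.

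**Working it through.** **1. What a literal reading does in the analysis.** A randomised participant is taken out under 6.2.1 without withdrawing consent.

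- Analysis set: SAP 2.2 keeps the participant in the FAS as randomised. No exclusion names an ARO decision.
- CV death and first HF hospitalisation: SAP 2.5.2.1 and 2.5.2.2 censor at the last visit. SAP 2.6.2.5 carries this to the secondary endpoints.
- Pairwise comparison: SAP 2.5.2 compares two participants only up to the censoring time.
- NT-proBNP: if the Week 12 value is missing, SAP 2.5.2.3 makes every pair that reaches this step a tie.

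What is lost is follow-up time and possibly one biomarker value. Membership of the analysis is not lost.

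**2. The plan's own event count.** Inputs from Protocol 12.8.1: 450 per arm, rates r of 0.20 and 0.16 per year, follow-up uniform from 1.5 to 3 years. With exponential event times,

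P = 1 − [exp(−1.5r) − exp(−3r)] / (1.5r)

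- Enalapril: 1 − (0.7408 − 0.5488)/0.30 = 0.360; × 450 = 162.0
- Sacubitril/valsartan: 1 − (0.7866 − 0.6188)/0.24 = 0.301; × 450 = 135.3
- Total 297.3 against the stated 302, a difference of 1.6%. The rates are reproduced.

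**3. The plan's power, approximately.** Simulation of an unstratified win ratio with a U-statistic standard error, 600 runs.

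- Enalapril hazards: HF hospitalisation 0.66 × 0.20 = 0.132, CV death 0.34 × 0.20 = 0.068.
- Hazard ratio 0.8 for both; NT-proBNP geometric mean ratio 0.75 with the 0.75 margin.
- Success as in Protocol 12.8.1: a significant win ratio and both estimated hazard ratios below 1.

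The SD of the log NT-proBNP ratio is not in the documents. Assumed SDs of 0.5 to 1.1 give 82–83% power, and 1.3 gives 79%, against the stated 85%. Monte Carlo error is about 1.5 points.

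**4. Effect of early exit.** The exit rate is also not in the documents, so these are assumed ranges, at SD 0.9. Percentages are of the arm named.

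| Planned effect true | Win ratio | Power | Events |
|---|---|---|---|
| No exit | 1.37 | 83% | 297 |
| Unrelated to outcome, 2–10%, one or both arms | 1.37 | 81–86% | 289–296 |
| Just before first event, 2% / 5% of both arms | 1.39 / 1.41 | 84% / 83% | 279 / 253 |
| Just before first event, 2% / 5% of enalapril only | 1.33 / 1.28 | 72% / 47% | 290 / 275 |
| Just before first event, 2% / 5% of sacubitril/valsartan only | 1.43 / 1.52 | 91% / 97% | 288 / 275 |

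The 81–86% spread in the second row is mostly Monte Carlo noise.

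With no true effect (1,500 runs, Monte Carlo error about 0.4 points near 2.5%), the one-sided win-ratio error is:

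- no exit: 2.8%
- exit unrelated to outcome, 2% of either arm or 5% of sacubitril/valsartan: 2.1–2.7%
- exit just before the event, sacubitril/valsartan only: 5.1% at 2% and 16.9% at 5%
- exit just before the event, enalapril only, 2%: 1.4%

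A second simulation used SD 0.6, a CV-death rate of 0.20 per year after HF hospitalisation, and removal one month before the first event. It agrees on the worst case: removing 8 of 450 sacubitril/valsartan participants (1.8%) raises the error from 2.6% to 4.5%.

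**The case against.** The strongest reply is that 6.2.1 is loosely worded and gives no real power of removal. It is a consultation step for cases of doubt. Protocol 9.1.1 itself speaks of continuing in the study within a list of reasons for stopping treatment, so the same slip may have occurred in 6.2.1. Protocol 3.2.2, 6.5 and 9.1.1 state the controlling rule plainly. For screened but unrandomised people there is no conflict at all. This stands as to intent, which the documents do not settle. It does not remove the conflict, because a site can act on the sentence as written.

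A reader might infer that switches to an ACEI, an ARB or commercial sacubitril/valsartan drive participants out through 6.2.1, and so differently by arm. The documents do not support this. Those drugs are not doubtful: Protocol 6.2.2 names them ("Concomitant use of open-label ACEIs, ARBs, commercially available sacubitril/valsartan, or renin inhibitors is strictly prohibited while the participant is receiving study drug") and gives a consequence for study drug only, and 6.2.3 allows them once study drug is stopped. The list is the same for both arms. Arm-related exit remains possible, since investigators are open label and Table 4-1 shows different hypotension rates in the earlier trial (17.61% against 11.97%), but it is not shown.

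A reader might also infer that the ARO must learn the arm to answer a query. Protocol 4.1 describes its study team as blinded, and judging whether a drug is prohibited does not require knowing the allocation. A particular query might reveal it; no passage shows that it does.

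**Conclusion.** The conflict between 6.2.1 and the other sections is established from the text and is worth correcting. Its consequence, if 6.2.1 is followed literally, is early censoring and possibly a missing Week 12 NT-proBNP value, contrary to the treatment-policy estimand. It is not removal from the primary analysis.

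The size of any bias is unknown. The documents give neither a rate of such exits nor any sign that one has occurred. Exit unrelated to prognosis has a negligible effect, and outcome-related exit balanced across arms moves the win ratio only slightly. A material effect needs exits that are both concentrated in one arm and timed shortly before events; its direction then depends on the arm. The error rates of about 5% and 17% rest on that extreme pattern, on an assumed NT-proBNP SD of 0.9, and on an unstratified analysis in place of the country-stratified bootstrap in SAP Appendix 4.1. They bound the problem from above for the exit rates assumed and should not be read as this trial's type I error.

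**What to change.** - Reconcile Protocol 6.2.1 with 9.1.1. After randomisation, the query to the ARO should concern the concomitant drug and study drug only. Whatever is decided on those, the participant stays in follow-up for all visits, endpoint collection and the Week 12 NT-proBNP sample unless consent is withdrawn. This changes no treatment rule.
- In SAP 2.3.1, add a disposition row by arm for follow-up ended by an investigator or ARO decision.
- For any such case on record, obtain vital status and HF hospitalisations to study end where consent still stands.

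Cost: a small amendment or clarification, one table row, and tracing of any affected participants. Protocol 14.1 requires sponsor and ethics approval for protocol changes, and health authority approval where required. SAP 2.1.2, in a version dated April 2025, already describes randomisation in the past tense, so new wording may come too late for participants already handled. The disposition row and the outcome recovery are then the useful part.
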